## **Corr Study Milestones and Procedures**

### **Informed Consent**

Informed consent will be obtained from potential participants (or their substitute decision maker where fully informed consent cannot be ascertained due to language or cognitive impairment) prior to beginning any study related activities.

Informed consent may be done in-person or virtually via RedCap e-consent, as per UHN's standard operating procedures for e-consent, depending on the participant's preference.

The informed consent process will involve an individual discussion with the participant about the nature of study procedures, interventions and assessments. A research team member will also explain reasonably anticipated benefits and potential hazards of the trial and any discomfort it may entail as well as alternatives to participating in the study.

The study team will be explaining and discussing the details in a language that is easy to comprehend. Participants will be encouraged to ask questions and take their time to consider and discuss the study with their families and healthcare providers. The study team will emphasize that participation is voluntary and refusal to participate in the study will not affect the quality of medical care. Participants will be informed that they are free to withdraw consent to participate at any time.

Participants will be informed that their medical and demographic data (glioma grade, time since diagnosis, tumour location, neurological deficits, prior occurrence(s) of tumour, other medical diagnoses, medications, current participation in neuro-rehabilitation and place of residence) that is necessary for conducting the study will be collected and that personal information will be treated as strictly confidential and will not be publicly available.

Participants will be informed in writing that their medical and social data relevant to this study will be stored and analyzed while maintaining confidentiality in accordance with local data protection laws. All data transferred to the eCRF (electronic Case Report Form) and any process derived from the eCRF will be deidentified.

A paper or an electronic informed consent form approved by the institutional Research Ethics Board (REB) will be reviewed, signed and dated by the participant and/or participant's substitute decision maker on one side and a delegated research team member on the other side. Participants will be provided with a copy of the signed informed consent form.

If new information becomes available that may be relevant to participants' willingness to stay in the study, the research team will inform the participants in a timely manner.

Should a protocol amendment be made, the informed consent form may be revised to reflect the changes in the protocol. In this case, the investigator will ensure that an amended informed consent form is reviewed and approved by the institutional REB, and that it is signed by all participants subsequently entered in the study and those currently in the study, if affected by the amendment.

An honorarium will also be provided as a token of appreciation for participants' time in the form of a \$50 gift card to a grocery store/book store after the 8-week and another \$50 gift card after the 26-week evaluations.

## **Baseline Evaluation**

At baseline, prior to the intervention beginning, the following data will be collected over video conferencing or as a self-administered questionnaire:

1. Participant Demographic Information Form

- 2. Participant Personal Information Form
- 3. Berg Balance Scale
- 4. Timed Up and Go Test
- 5. 30 Sec Sit to Stand Test
- The Arm Capacity and Movement Test (ArmCAM)
- 7. Brief Test of Adult Cognition by Telephone (BTACT)
- 8. Brief Visuospatial Memory Test Revised (BVMT)
- 9. Sustained Attention to Response Task (SART)
- 10. Wechsler Test of Adult Reading (WTAR)
- 11. Perceived Medical Condition Self-Management Scale
- 12. EuroQol-5 Dimension 5 Level (EQ-5D-5L)
- 13. Fatique Severity Scale

#### 4-Week Evaluation

At the 4-week evaluation, we will collect the following data over video conferencing or as a self-administered questionnaire:

- 1. Berg Balance Scale
- 2. Timed Up and Go Test
- 3. 30 Sec Sit to Stand Test
- 4. The Arm Capacity and Movement Test (ArmCAM)
- 5. Brief Test of Adult Cognition by Telephone (BTACT)
- Brief Visuospatial Memory Test Revised (BVMT)
- 7. Sustained Attention to Response Task (SART)
- 8. Wechsler Test of Adult Reading (WTAR)
- Perceived Medical Condition Self-Management Scale
- 10. EuroQol-5 Dimension 5 Level (EQ-5D-5L)
- 11. Fatigue Severity Scale
- 12. Medical Information Update Form

#### 8-Week Evaluation

At the 8-week evaluation, we will collect the following data over video conferencing or as a self-administered questionnaire:

- 1. Berg Balance Scale
- 2. Timed Up and Go Test
- 3. 30 Sec Sit to Stand Test
- 4. The Arm Capacity and Movement Test (ArmCAM)
- 5. Brief Test of Adult Cognition by Telephone (BTACT)
- 6. Brief Visuospatial Memory Test Revised (BVMT)
- 7. Sustained Attention to Response Task (SART)
- 8. Wechsler Test of Adult Reading (WTAR)
- 9. Perceived Medical Condition Self-Management Scale
- 10. EuroQol-5 Dimension 5 Level (EQ-5D-5L)
- 11. Fatigue Severity Scale
- 12. Medical Information Update Form

Any new medical diagnoses, adverse events, or changes in other medications will be noted.

## 12-Week Evaluation

At the 12-week evaluation, we will collect the following data over video conferencing or as a self-administered questionnaire:

- 1. Berg Balance Scale
- 2. Timed Up and Go Test
- 3. 30 Sec Sit to Stand Test
- 4. The Arm Capacity and Movement Test (ArmCAM)
- 5. Brief Test of Adult Cognition by Telephone (BTACT)
- 6. Brief Visuospatial Memory Test Revised (BVMT)
- 7. Sustained Attention to Response Task (SART)
- 8. Wechsler Test of Adult Reading (WTAR)
- 9. Perceived Medical Condition Self-Management Scale
- 10. EuroQol-5 Dimension 5 Level (EQ-5D-5L)
- 11. Fatigue Severity Scale
- 12. Medical Information Update Form

Any new medical diagnoses, adverse events, or changes in other medications will be noted.

#### 26-Week Evaluation

At the 26-week evaluation, we will collect the following data over video conferencing or as a self-administered questionnaire:

- 1. Berg Balance Scale
- 2. Timed Up and Go Test
- 3. 30 Sec Sit to Stand Test
- 4. The Arm Capacity and Movement Test (ArmCAM)
- 5. Brief Test of Adult Cognition by Telephone (BTACT)
- 6. Brief Visuospatial Memory Test Revised (BVMT)
- 7. Sustained Attention to Response Task (SART)
- 8. Wechsler Test of Adult Reading (WTAR)
- 9. Perceived Medical Condition Self-Management Scale
- 10. EuroQol-5 Dimension 5 Level (EQ-5D-5L)
- 11. Fatigue Severity Scale
- 12. Medical Information Update Form
- 13. Semi-structured Interview about participant experiences with telerehab for those in the intervention group

Any new medical diagnoses, adverse events, or changes in medications will be noted.

The evaluators will be trained neuropsychologists/psychometrists, physiotherapists and occupational therapists. The participant's privacy during evaluations will be ensured by the use of pass codes to access the videoconference, personalized links or each participant to avoid unwanted participants, restricting screensharing to the evaluator, using the Lobby feature in Microsoft Teams, and the evaluators checking at the start of the evaluations if the participant is ok with their caregivers hearing the answers to questions asked.

## Outcome Measurements

## **Primary Outcome**

The primary outcome is feasibility of the intervention as measured by the percentage of participants who complete the intervention at week 8.

## **Secondary Outcomes**

- Recruitment Screening and recruitment efficiency, number of participants recruited, percentage of patients approached who consent to the trial
- 2. **Adherence to interventions** Percentage of rehab sessions attended, participant characteristics associated with adherence, percentage of participants who used BrainHQ/exercise programs and how much
- 3. **Retention** Follow-up rates, time needed for data collection
- 4. **Participant Experience** We will conduct semi-structured qualitative interviews with participants to better understand their telerehab experiences, the perceived impact of the intervention on quality of life, and barriers/facilitators for their participation in the intervention.

**Safety** - percentage of patients who experience adverse events, percentage of rehab sessions in which adverse events occurs, and adverse event type, severity and relatedness across both intervention groups.

## **Explanatory Variables to Characterize the Population:**

Demographic and medical variables to characterize the participant population will be collected at baseline and will include age, sex/gender, place of residence, education, postal code, occupation, race and ethnicity, presence of caregiver at residence, duration of radiation therapy, and medical comorbidities and medications. To reduce the time demands placed on participants, a research assistant will collect the variables whenever possible from chart review, and ask participants to provide information on the variables not available from chart review.

Table 1. Measurement Tools and Testing Schedule

Base-	4W	W8	12W	26W
line	`	(100	(100	(160
(100	min)	min)	min)	min)
min)				

Participant Demographic and Medical Information Form	Х				
Participant Personal Information Form	Х				
General Outcomes					
Feasibility and Safety Outcomes		Х	Х	Х	Х
Survival and Progression-Free Survival		Х	Х	Х	Х
EuroQol-5 Dimension 5 Level (EQ-5D-5L)	Х	Х	Χ	Х	Х
Fatigue Severity Scale	Х	Х	Χ	Х	Х
Physical outcomes measures					
Berg Balance Scale	Χ	Х	Χ	Х	X
Timed Up and Go Test	Χ	X	Χ	X	X
3m Walk Test	Х	X	Χ	X	X
The Arm Capacity and Movement Test (ArmCAM)	Х	Х	Χ	Х	Х
Cognitive tests					
Brief Test of Adult Cognition by Telephone (BTACT)	Х	Х	Χ	Х	Х
Brief Visuospatial Memory Test – Revised (BVMT)	Х	Х	Х	Х	Х
Sustained Attention to Response Task (SART)	Х	Х	Х	Х	Х
Wechsler Test of Adult Reading (WTAR)	Х	Х	Χ	Х	Х
Qualitative component					
Semi-structured Interview (telerehab group only)					Х

The majority of our outcome measures are self-report measures, which participants can either complete themselves and/or with assistance from a helper or research study staff based on participants' preferences. The outcome measures can be administered via a REDCap survey link sent to participants to enter their answers directly into REDCap or with assistance from a helper if they need it or via an online videoconference or telephone call between participants and study staff for direct entry of participants' answers into REDCap by research study staff (whichever method participants prefer).

#### **Telerehab Intervention Protocol**

Participants randomized into the active intervention group will be asked to participate in an outpatient neuro-rehabilitation program via telerehabilitation starting **concurrently** with their radiation therapy. Currently, patients with gliomas with rehabilitation needs start rehabilitation after their radiation therapy. The neuro-rehabilitation program used in the study will be 8-weeks in duration, and identical to what we currently offer in the ABI day hospital with the exception of 1) the rehabilitation program start concurrently with radiation and 2) the

therapies will delivered via telerehabilitation for all participants (compared to the ABI day hospital currently delivers up to 1/3 of their therapy sessions via telerehabilitation.

The key components of the outpatient neuro-rehabilitation program in this study are:

- Participants will discuss with the ABI day hospital service coordinator their impairments and goals, to understand if they need physiotherapy, occupational therapy and/or speech language therapy based on their clinical needs
- They will have twice a week, 50min sessions for each type of therapy
- Therapy will be delivered via Microsoft Teams and/or phone, based on therapists' clinical judgment

## Adherence to telerehab protocol:

Adherence will be monitored using the Encounters data in EPIC, which displays "no-show" data to therapy sessions were attended. >80% attendance will be considered adherence to the telerehab protocol.

#### Risks related to telerehab:

Risk of falls, injury and cardiac events such as dysrhythmia, exertional angina, and muscular/joint strains. Telerehab groups will be supervised and emergency contact information will be provided by participants. Participants will obtain physician clearance for exercise and will have a caregiver present during telerehab sessions. All telerehab sessions provided as part of this study will be provided by specialized physiotherapists, occupational therapists and speech language pathologists with training in neuro-rehabilitation working in the Brain Rehab program, and they will be adhering to all Brain Rehab Program policies and procedures on safety during telerehab.

Principal Investigators will review and classify all adverse events as to severity, whether it was expected or not, and whether it was related to the intervention. Recruitment rate, dropouts at all stages, and reasons for non-completion will also be tracked.

Adverse events related to the telerehabilitation assignment or to other causes will be adjudicated by the PIs.

## **Study Sample Size and Statistical Analysis Sample Size**

A sample of 54 participants, 27 per arm, is planned for this study based upon an expected recruitment rate of a third (33%) of glioma patients seen in recruiting clinics (163 patient per annum). Feasibility trials are recommended to recruit between 20 to 50 participants per arm to adequately investigate if a protocol is feasible or not and a minimum of 22 participants per arm is required for precision

of the variance estimation. Loss to follow-up (LOF) will be analyzed as the primary outcome and the sample size will not be adjusted for LOF.

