## **Statistical Analysis Plan**

## Primary Outcome

The primary outcome of the study is the feasibility of the protocol as defined as ≥80% of participants completing the 8-week protocol. It will be measured by percentage completed the 8-week protocol. If more than or equal to 80% of participants complete the 8-week protocol it will be deemed feasible. Rates of completion will also be compared by treatment arm at the Week 8 time point. Adherence to the study protocol will also be measured as attendance to telerehab sessions and ≥80% attendance will be defined as adherent. Percentage deemed adherent will be compared between the treatment arms at the 8-week time point.

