## Secondary Outcomes

Secondary outcomes (e.g. balance, mobility, quality of life, mood, etc.) are continuous in nature and will be analyzed using linear regression, adjusted for baseline. Time to all-cause mortality, time to disease specific mortality, and time to disease progression will be analyzed using Kaplan Meier estimators and logrank tests.

Disease and demographic factors that may influence protocol attrition and adherence will be analyzed using a generalized linear mixed effects model with an assumed unstructured covariance matrix structure and robust sandwich estimation.

To assess the safety of the protocol, the number, type, and severity of SA events will be reported as a cumulative incidence and compared between treatment arms using a Poisson regression.

Since these analyses are hypothesis generating, complete-case analyses will be used, p-values will not be listed and 95% confidence intervals of estimates and change scores will be used instead so the study results can be interpreted in context. The standard deviation of changes in secondary outcome measures will be used for sample size calculations for future full-scale studies.

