## **Documenting participant withdrawal**

In all circumstances, reasons for withdrawal will be collected and all participants will be followed through to the trial's conclusion with previously stated outcome measures performed (timing is outlined in Table 1), as the main analysis will be an intention to treat analysis. This will, of course, be subject to the participant's continued consent to return for these assessments. Participants who withdraw consent will be advised to follow up with their regular health care provider.

Participants who are withdrawn or withdraw from active treatment will not be replaced.

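### The stated minimum of 22 per arm for variance estimation has no real margin for loss: 27 per arm does not reliably leave 22 analysed, and the reason for making no allowance does not apply to the SDs

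*Protocol*

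**What the plan says.** The Protocol's sample size section states: "A sample of 54 participants, 27 per arm, is planned for this study". The total rests on expected recruitment, a third of 163 patients a year. As support, the section cites a recommended range of 20 to 50 per arm for feasibility trials and adds that "a minimum of 22 participants per arm is required for precision" of the variance estimation. It closes by saying that loss to follow-up is analysed as the primary outcome and that "the sample size will not be adjusted for LOF".

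Three other places bear on this:

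- Statistical Analysis Plan, Primary Outcome: "If more than or equal to 80% of participants complete the 8-week protocol it will be deemed feasible".
- Statistical Analysis Plan, Secondary Outcomes: "complete-case analyses will be used, p-values will not be listed", and "The standard deviation of changes in secondary outcome measures will be used for sample size calculations for future full-scale studies". The Missing Data section confirms that only complete cases are used, even when more than 5% of data are missing.
- Documenting participant withdrawal: those who withdraw are not replaced, but "all participants will be followed through to the trial's conclusion with previously stated outcome measures performed", subject to their consent.

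**The concern.** Two statements that stand next to each other concern different quantities. The minimum of 22 is about the precision of a variance. The waiver of any loss allowance is justified by a property of the completion percentage.

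For the completion percentage the waiver is sound: a participant who is lost counts as a non-completer and stays in the denominator. A change-score SD needs a baseline and a follow-up value, so every participant without follow-up data drops out of it. Making loss an outcome does nothing to protect that estimate.

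The SDs of change are the figures that the Protocol hands on to the design of full-scale studies. A reader of the sample size section would take them to rest on at least 22 per arm, a property that the design does not reliably have.

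**Working it through.** **Inputs from the Protocol.** 54 randomised 1:1, so 27 per arm; minimum 22 per arm; no allowance for loss; no replacement; complete cases for the SDs; success at 80% or more completing at week 8.

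**Assumptions.** Non-completers give no outcome data (relaxed in step 5). Participants complete independently, with the same true rate in both arms.

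**1. The planned total.** 163 × 0.33 = 53.8 and 163 / 3 = 54.3, so 54 is reproduced. No derivation is given for 22, so it is taken as stated.

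**2. Margin over 22.** 27 − 22 = 5, and 5 / 27 = 18.5%. An arm keeps 22 only if its retention is at least 22 / 27 = 81.5%. The feasibility rule accepts up to 20% non-completion. At exactly 80% the expected number is 27 × 0.80 = 21.6. Usual inflation for 20% loss gives 22 / 0.80 = 27.5, so 28 per arm.

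**3. Chance of keeping 22.** With X ~ Binomial(27, p), P(one arm) = P(X ≥ 22), and P(both arms) is its square.

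| True completion p | Expected per arm | P(one arm ≥ 22) | P(both ≥ 22) |
|---|---|---|---|
| 75% | 20.25 | 0.30 | 0.09 |
| 80% | 21.6 | 0.54 | 0.29 |
| 85% | 22.95 | 0.79 | 0.62 |
| 90% | 24.3 | 0.95 | 0.91 |

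**4. Given that the target is met.** The target is an observed count. 43 / 54 = 79.6% fails and 44 / 54 = 81.5% passes. If both arms reach 22 the total is at least 44, so P(both ≥ 22 | target met) = P(both ≥ 22) / P(total ≥ 44).

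- True rate 80%: 0.290 / 0.473 = 0.61.
- True rate 85%: 0.625 / 0.822 = 0.76.
- True rate 90%: 0.908 / 0.983 = 0.92.

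With exactly 44 completers and equal true rates, the split is 22/22 with probability C(27,22)² / C(54,44) = 0.27. Otherwise one arm is short.

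**5. Non-completers who still attend assessments.** At 80% completion, if a quarter of non-completers supply data, the data rate is 0.80 + 0.20 × 0.25 = 0.85 and P(both ≥ 22) = 0.62. If half do, the rate is 0.90 and P(both ≥ 22) = 0.91.

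**6. Effect on the SD at week 8.** The 95% interval for a true SD runs from √((n−1)/χ²₀.₉₇₅) to √((n−1)/χ²₀.₀₂₅) times the estimate, with n−1 degrees of freedom.

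- n = 22 in one arm: 0.77 to 1.43.
- n = 21 in one arm: 0.77 to 1.44.
- Pooled over two arms of 22, 42 degrees of freedom: 0.82 to 1.27.

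**7. Later visits.** The Protocol gives no retention figure for weeks 12 or 26. As assumptions, 70% leaves 27 × 0.70 = 18.9 per arm and 60% leaves 16.2.

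**The case against.** A reader might infer that 27 per arm cannot deliver 22 even when the 80% target is met. The documents do not support that. The smallest passing count, 44 of 54, is exactly 22 per arm if evenly split, and once the target is met both arms are more likely than not to reach 22 (step 4). The figure of 0.29 belongs to a true rate of 80%, at which the target itself is met only 47% of the time.

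Other points on that side:

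- **The sample size section contains no wrong sum.** The total is openly based on recruitment, 27 exceeds 22, and the decision not to adjust is disclosed with its reason. This stands. The fault lies in the reasoning, not in the arithmetic.
- **The section does not say whether 22 means recruited or analysed.** If it means recruited, 27 satisfies it. But a recruited number says nothing about the precision of an SD taken from complete cases, so the stated purpose makes sense only for an analysed number. The ambiguity needs resolving either way.
- **Stopping the intervention is not the same as having no data.** Withdrawn participants are still followed if they consent, so one-for-one loss is a worst case. This stands, and step 5 shows how much it helps. It cannot help for participants who die, and the Protocol plans mortality analyses.
- **The practical loss at week 8 is very small.** This stands: 0.4 of a participant on expectation, with almost no change in the interval for the SD.
- **Lower retention at later visits is not documented.** It is plausible, but the Protocol gives no figure and does not tie 22 to those visits. The numbers in step 7 are therefore illustrations.

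**Conclusion.** The concern holds in a limited form. The Protocol states a minimum for variance estimation and waives any loss allowance for a reason that does not apply to that estimate. With 27 per arm and no replacement, 22 analysed per arm is possible but not reliable: at a true 80% rate both arms reach it with probability 0.29, or 0.61 once the observed target is met. These figures assume that non-completers give no data and that the arms share one completion rate.

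At week 8 the consequence for precision is trivial. It would be larger at weeks 12 and 26 if retention there is well below 81.5%, which the Protocol neither states nor rules out. It would be wrong to conclude that the trial is too small for its primary purpose: feasibility is judged on everyone randomised, and this point does not touch it.

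**What to change.** Keep N = 54 and amend the text.

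1. In the sample size section, say that 22 is an analysed number and name the visit. Add that 27 per arm gives about 21 to 22 per arm at week 8 with 80% retention, and fewer at later visits if retention is lower.
2. Drop the implication that having loss as the primary outcome removes the need for an allowance. Say instead that the total is set by recruitment and that the precision of the SDs will depend on retention.
3. In the Secondary Outcomes analysis text, estimate each SD of change pooled over arms (about 42 degrees of freedom at week 8) and report it with its actual n and 95% confidence interval.

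The cost is wording only, with no extra participants. The stated precision basis becomes slightly less favourable, and pooling assumes similar SDs in the two arms, which can be checked by also showing the SDs by arm. How a later trial allows for uncertainty in the SD is a choice for that trial and need not be fixed here.
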